#### 5.5 Contraception requirements for women of childbearing potential

#### 5.5.1 Definition of childbearing potential

A woman is considered to be of childbearing potential, i.e., fertile, following menarche and until becoming post-menopausal unless permanently sterile.

Permanent sterilization methods include hysterectomy, bilateral salpingectomy, and bilateral oophorectomy.

Post-menopausal state is defined as 12 consecutive months with no menses without an alternative medical cause (ICH M3 definition).

#### 5.5.2 Methods of contraception

WOCBP [see definition in Section 5.5.1] must use a highly effective contraceptive method from Screening visit up to 30 days after study treatment discontinuation.

Contraceptive methods with low user dependency should preferably be used, particularly when contraception is introduced as a result of participation in the study.

Highly effective contraceptive methods are defined as those, alone or in combination, that result in a failure rate of less than 1% per year when used consistently and correctly. Such methods include:

- 1. Hormonal contraceptives: Combined (containing estrogen and progestogen) or progestogen-only hormonal contraception associated with inhibition of ovulation using one of the following routes of administration:
  - a. Oral
  - b. Intravaginal
  - c. Transdermal
  - d. Injectable
  - e. Implantable (low user dependency)

If a hormonal contraceptive is chosen from this group, it must be taken for at least 30 days prior to administration of the first study treatment dose. If during the study treatment period a study participant switches, or starts, a hormonal contraceptive method, additional contraceptive protection may be required to ensure a highly effective contraceptive method is used without discontinuation.

Hormonal contraception from the above list must be used in conjunction with a supplemental barrier. The acceptable supplemental barrier methods to be used in conjunction with hormonal contraception are: male condom (preferred method), female condom, cervical cap, or diaphragm. Cervical cap and diaphragm must be used in combination with a spermicide. In countries in which spermicides are not available/authorized, cervical cap and diaphragm must not be used.

- 2. Intrauterine device (low user dependency).
- 3. Intrauterine hormone-releasing system (low user dependency).
- 4. Bilateral tubal occlusion/ligation at least 6 weeks prior to Screening visit (low user dependency).

- 5. Vasectomized partner; this is a highly effective birth control method provided that the partner is the sole sexual partner of the WOCBP study participant and that the vasectomized partner has received medical assessment of the surgical success.
- 6. Sexual abstinence, defined as refraining from heterosexual intercourse during the entire period of risk associated with the study treatment(s). The reliability of sexual abstinence needs to be evaluated in relation to: the duration of the clinical study; whether it is the preferred and usual lifestyle of the study participant; and whether it is locally accepted as a highly effective method of contraception.

The following contraception schemes used alone are NOT considered as highly effective methods of contraception:

- Male or female condom with or without spermicide.
- Cap, diaphragm, or sponge with or without spermicide.

The following methods are NOT ALLOWED as methods of contraception for this study:

- Progestogen-only oral hormonal contraception (except if inhibition of ovulation is the primary mode of action).
- Periodic abstinence (calendar, symptothermal, post-ovulation methods).
- Withdrawal (coitus interruptus).
- Spermicides only.
- Lactational amenorrhea method.
- Combination of female condom and male condom.

If the investigator/delegate finds that the protocol-mandated highly effective method of contraception is not consistently and correctly followed by the study participant, the study treatment **must** be permanently discontinued [see Section 5.9.1.2].

Note: The documentation of method of contraception can be based on the site personnel's review of the study participant's medical records, medical examination, or medical history interview of the study participant.

# 5.6 Contraception for male study participants with WOCBP partner

No contraceptive methods are needed for male study participants participating in this clinical study.

# 5.7 Dietary aspects and physical activity restrictions

During the study, study participants will be instructed to:

- Refrain from consumption of grapefruit, grapefruit hybrids, Seville orange, pomelos, pomegranates, and star fruits, and their juices from 2 weeks before the start of study treatment until the last dose of study treatment.
- Abstain from strenuous exercise before each blood collection for clinical laboratory tests.
- Refrain from consuming alcohol > 2 drinks a day.
- A drink is defined as:
  - a. A bottle/can of 33 cl / 12 ounces of beer (~14 grams alcohol)
  - b. A glass of 10-12 cl / 4 ounces of wine ( $\approx 12$  grams alcohol)
  - c. A small glass of 3-4 cl / 1 ounce of liquor ( $\approx 9$  grams alcohol)
- Refrain from engaging in hazardous activities that require complete mental alertness, such as driving or operating heavy machinery, following study treatment intake until fully alert and comfortable to do so.

# 5.8 Screen failures and re-screening

Screen failures are defined as participants recruited in the clinical study (i.e., ICF fully signed) but not subsequently enrolled in the study. Minimum information includes demography, medical history, screen failure details (i.e., reason for screen failure), BE diary data, concomitant medication, adverse events and eligibility criteria not met.

It is not permitted to re-screen study participants in this study.

# 5.9 Criteria for withdrawal of study participants

A study participant has the right to prematurely discontinue study treatment at any time, by withdrawing from study treatment only or by withdrawing from study treatment and any further participation in the study (i.e., premature withdrawal from the study). It is recommended that the investigator/delegate makes a reasonable effort to maintain study participants on treatment, as medically appropriate, and follow the schedule of visits, since data robustness depends on such compliance. Should a study participant stop treatment or withdraw from the study, the investigator/delegate should ascertain the reason(s), while fully respecting the study participant's rights.

Study participants who prematurely discontinue study treatment, or the study, for any reason will not be replaced.

#### 5.9.1 Study treatment premature discontinuation

The decision to prematurely discontinue study treatment may be made by the study participant, the investigator/delegate, or the sponsor personnel.

The investigator/delegate has the option of prematurely discontinuing study treatment for a given study participant in response to an AE, a diagnostic or therapeutic procedure, a laboratory abnormality, or for administrative reasons. If study treatment is interrupted by the study participant for any reason, she/he must inform the investigator/delegate as soon as possible. Study treatment dose interruptions must be recorded in the eCRF.

The investigator/delegate must permanently discontinue study treatment for a given study participant if, on balance, he/she believes that continued administration would be contrary to the best interests of the study participant.

Study-specific criteria for permanent discontinuation of study treatment are described in Sections 5.9.1.1 to 5.9.1.4.

The main reason for permanent discontinuation of study treatment (e.g., due to pre-specified study treatment discontinuation criteria, an AE, lack of efficacy, study termination) must be documented in the eCRF.

A study participant who prematurely discontinues study treatment is not considered as withdrawn from the study.

The study participant who prematurely discontinues study treatment or who is permanently discontinued from study treatment will be asked to return for an EOT visit within 1 to 5 days of last intake of study treatment and thereafter to attend follow-up visits as defined in the schedule of activities [Table 1, Section 7.2].

# 5.9.1.1 Pregnancy

If a study participant becomes pregnant while on study treatment, study treatment must be permanently discontinued. The investigator/delegate must counsel the study participant and discuss the risks of continuing with the pregnancy and the possible effects on the fetus. For reporting of pregnancies, refer to Section 8.3.1.

#### 5.9.1.2 Lack of compliance with methods of contraception

If the investigator/delegate considers that the study participant is not compliant with the protocol instructions on methods of contraception; study treatment must be permanently discontinued.

#### 5.9.1.3 Liver aminotransferase abnormalities

If ALT or  $AST \ge 3 \times ULN$  and  $< 8 \times ULN$ , a re-test of aminotransferases, total and direct bilirubin, and alkaline phosphatase must be performed within 7 calendar days. If the aminotransferase values return to pre-treatment levels or within normal ranges, study treatment can be continued. If AST or ALT elevation is confirmed, study treatment must be stopped and not re-introduced. Aminotransferases, total and direct bilirubin, and

alkaline phosphatase levels must be monitored at least once every 7 calendar days until values return to pre-treatment levels or within normal ranges.

Study treatment must be stopped, and its reintroduction is not to be considered in the following cases:

- Aminotransferases  $\geq 8 \times ULN$
- Aminotransferases ≥ 3 × ULN and associated clinical symptoms of liver injury, e.g., nausea, vomiting, fever, abdominal pain, jaundice, unusual lethargy or fatigue, flu-like syndrome (arthralgia, myalgia, fever)
- Aminotransferases  $\geq 3 \times ULN$  and associated increase in total bilirubin  $\geq 2 \times ULN$

Aminotransferases, total and direct bilirubin, and alkaline phosphatase levels must be monitored at least once every 7 calendar days after study treatment discontinuation until values return to pre-treatment levels or within normal ranges.

Furthermore, other diagnoses (e.g., viral hepatitis, mononucleosis, toxoplasmosis, cytomegalovirus, alcoholic hepatitis, non-alcoholic steatohepatitis, autoimmune disease) and/or etiologies (e.g., hepatic toxicity of concomitant medication[s] or other substances) should be considered and ruled out by performing the appropriate tests.

All liver aminotransferases abnormalities leading to study treatment discontinuation must be recorded as AEs [see Section 8.1.1].

#### 5.9.1.4 COVID-19

# *Provisions for study participants infected with SARS-CoV-2 or quarantined due to pandemic*

Testing for SARS-CoV-2 should follow local guidance. Mandatory testing is not required for this study; however, standards for testing and management should be followed according to local and site-specific guidelines.

Should a study participant become infected with SARS-CoV-2 / contract COVID-19, or should a study participant be quarantined:

- Information about COVID-19 infection, whether positively confirmed with a SARS-CoV-2 test or not, and its corresponding diagnosis (including pneumonia related to COVID-19), symptoms, as well as administered medications, will be collected on the AE and Concomitant Medication pages of the eCRF.
- If a study participant is without symptoms and remains asymptomatic, study treatment can be continued as per protocol.

- If a study participant presents with mild symptoms, study treatment can be continued as per protocol and the study participant should be closely monitored. Should the symptoms worsen, study treatment may be discontinued as per investigator judgment.
- If a study participant develops severe symptoms or requires hospitalization for COVID-19, the study participant must be discontinued from study treatment.
- When shipping blood samples from study participants who tested positive or have a high potential to test positive for SARS-CoV-2 virus infection to the study central laboratory, the central laboratory manual and the most up-to-date COVID-19 regional guidance should be followed.
- DDI with medications used to treat COVID-19: Certain treatments used for COVID-19, such as lopinavir/ritonavir (strong CYP3A4 inhibitor) are contraindicated in association with ACT-539313. Please refer to the IB for more details on potential DDIs with ACT-539313. If possible, such treatments should be avoided for at least 24 hours after the last dose of study treatment. Details of any medication given for COVID-19 management should be recorded in the eCRF under Concomitant medications.

# COVID-19 vaccination

COVID-19 vaccination with authorized vaccines, as per CDC and local guidelines, is allowed, provided the vaccination conditions set forth by the respective manufacturer (consistent with the respective prescribing information / package insert) are observed. Prior to any planned vaccination the study participant should, after consultation with his/her primary care physician, inform the investigator of such plan. Study visits and assessments should continue as planned if possible and appropriate as per investigator judgment. Receipt of the vaccine, and details thereof, should be recorded in the medical notes and in the eCRF under Concomitant medications.

General reporting of AEs should continue to be implemented as described in Section 8.2, including vaccination-related AEs, and reports of AEs for approved vaccines should be submitted as appropriate to the Vaccine Adverse Events Reporting System (VAERS) as per FDA guidance [FDA 2021].

# 5.9.2 Withdrawal from the study

Study participants may voluntarily withdraw from the study without justification for any reason at any time. Study participants are considered withdrawn if they state an intention to withdraw further participation in all components of the study (i.e., withdrawal of consent), die, or are lost to follow-up [see Section 5.9.3]. If a study participant withdraws consent for further study participation, no further data will be collected in the eCRF from the date of withdrawal onward. The investigator/delegate may withdraw a study participant from the study (without regard to the study participant's consent) if, on balance, he/she believes that continued participation in the study would be contrary to the best interests of

the study participant. Withdrawal from the study may also result from a decision by the sponsor for any reason, including premature termination or suspension of the study [see Section 10.10].

Enrolled study participants who prematurely discontinue from the study for any reason will not be replaced.

If, for whatever reason (except death or loss-to-follow-up), a study participant is withdrawn from the study, the investigator/delegate should make best efforts to schedule a last appointment / telephone call to assess the safety and well-being of the study participant, collect unused study treatment and discuss follow-up medical care. Data obtained during this last appointment / telephone call will be recorded in the study participant's medical records, but they will not be collected in the eCRF.

The main reason for premature withdrawal from the study must be documented in the eCRF.

The investigator must provide follow-up medical care for all study participants who are prematurely withdrawn from the study, or must refer them for appropriate ongoing care, as described in Section 6.3.

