# 8.2 **Reporting procedures**

# 8.2.1 Reporting and follow-up of AEs

The occurrence of an AE may come to the attention of study personnel during study visits, telephone calls, or interviews of study participants presenting for medical care.

At each study visit (scheduled or unscheduled), the investigator/delegate will inquire about the occurrence of AEs since the last visit.

All AEs with an onset date after signing of the ICF up to EOS must be recorded in the eCRF.

The AE should be reported as a final diagnosis (if possible) rather than a list of symptoms.

Information to be collected on an AE form in the eCRF includes date of onset, time of onset, action taken with the study treatment, outcome of the AE, date and time of resolution (if applicable), and PI/delegate's assessment of intensity as well as its relationship to study treatment or protocol-mandated procedures.

Information on worsening of intensity will be collected. If the AE lessens in intensity, no change in the severity is required to be reported.

AEs still ongoing after study treatment discontinuation must be followed up until resolution, until they are no longer considered clinically relevant, or until stabilization.

ACT-539313 Binge Eating Disorder Protocol ID-082A201 Final Version 3 4 May 2021, page 80/140

Confidential

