1 INTRODUCTION

This SAP describes in detail the analyses and data presentation for the CSR prepared for ID-082A201.

Obvious corrections to address minor formatting errors or spelling mistakes may be performed at the time of analysis without amending this and related documentation (e.g., mock shells).

Data will be analyzed by Idorsia and/or designated CROs supervised by Idorsia using SAS[®] version 9.4 or higher and R version 3.4.3 or higher.

This SAP is based on Version 3 of Protocol ID-082A201, dated 4 May 2021 [Table 1].

Table 1Study documents

Document	Date, Version	
Clinical Study Protocol (CSP)	04MAY2021, Version 3	
eCRF specifications	01FEB2021, Version 2	
Protocol deviation list	21JAN2022, Version 4	

During the drafting of the current SAP, three sites withdrew from the study due to financial reasons related to COVID-19: sites 1012, 1015, and 1061. Consequently, all study participants randomized in these sites discontinued treatment and finished the study. Section 6 describes how these study participants will be considered for the efficacy analyses.

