mnar model (OBST5 / modelobs=(TRT='PLACEBO'));
run;
```

```
/*** OBST6 ***/
```

```
proc mi data=data mi6 nimpute=1 seed=163882 minimum=...0 0 maximum=...77
out=data mi7 noprint;
by _IMPUTATION_; /* flag variable for imputation from proc mi */
class TRT SEX BMIGR;
var SEX BMIGR BASE OBST6;
monotone regression;
mnar model (OBST6 / modelobs=(TRT='PLACEBO'));
run;
```

un,

The 9 study participants forced to discontinue due to site closure will be imputed using MAR assumption setting the seed to 163882.

14.5 SAS[®] code for multiple imputation under MNAR assumption for the delta-adjusted tipping point method

This SAS[®] statement is used to perform multiple imputation under MNAR assumption after the dataset has being set to a monotone missingness pattern. Imputations are performed sequentially for each time point: Week 1–2 (OBST1) then Week 3–4 (OBST2) then Week 5–6 (OBST3) then Week 7–8 (OBST4) then Week 9–10 (OBST5) and finally Week 11–12 (OBST6). Assuming the data are in 'wide' format (i.e., one row for each subject with one variable for each visit) and with a monotone pattern, example SAS[®] statements for the implementation of the macro for delta-adjusted tipping point are:

```
/*** multiple imputation ***/
%macro midata(data=, smin=, smax=, sinc=, out=);
data &out;
    set null ;
run;
/*-----# of shift values -----*/
%let ncase= %sysevalf( (&smax-&smin)/&sinc, ceil );
```

```
ACT-539313
                                                               Statistical Analysis Plan
 ID-082A201
                                                              for Clinical Study Report
                                     Confidential
 1 April 2022, page 51/60
                                                                           Version 3
                                                                     Doc No D-22.100
/*-----Imputed data for each shift -----*/
%do jc=0 %to &ncase;
%let sj= %sysevalf( &smin + &jc * &sinc);
proc mi data=&data seed=295104 nimpute=1 minimum=...0000000 maximum=...
     7777777 out=outmi;
     by IMPUTATION ; /* flag variable for imputation from proc mi */
     class TRT ASEX BMIGR;
     monotone regression;
     mnar adjust(obst1 / shift=&sj adjustobs=(TRT = 'ACT-539313 100 mg'));
     mnar adjust(obst2 / shift=&sj adjustobs=(TRT = 'ACT-539313 100 mg'));
     mnar adjust(obst3 / shift=&sj adjustobs=(TRT = 'ACT-539313 100 mg'));
     mnar adjust(obst4 / shift=&sj adjustobs=(TRT = 'ACT-539313 100 mg'));

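### Protocol 5.9.2 keeps last-contact safety data out of the eCRF even where consent stands, which contradicts the rule in 8.2.1 that all AEs up to EOS are recorded

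*Protocol*

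**What the plan says.** Protocol 5.9.2 contains two separate data rules.

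- **Consent withdrawal.** "If a study participant withdraws consent for further study participation, no further data will be collected in the eCRF from the date of withdrawal" onward.
- **Last contact.** This rule opens "If, for whatever reason (except death or loss-to-follow-up), a study participant is withdrawn from the study". The site then tries to arrange a final appointment or call to check safety and well-being, collect unused study treatment and discuss follow-up care. What is learned goes into the participant's "medical records, but they will not be collected in the eCRF".

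The same section names routes out of the study that do not depend on the participant's wish. The investigator may withdraw someone, regardless of that person's consent, if continued participation is judged contrary to their best interests. Also, "Withdrawal from the study may also result from a decision by the sponsor for any reason".

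Other parts of the protocol point the other way. Section 8.2.1 states: "All AEs with an onset date after signing of the ICF up to EOS must be recorded in the eCRF". Table 1 footnote 7 asks for all AEs, SAEs and procedures over the same period to be reported. Section 6.1.6.4 has the inventory of returned study treatment entered in the eCRF.

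SAP 7.2 counts TEAEs from treatment start to EOS and tabulates those of the follow-up period separately.

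**The concern.** Stopping eCRF entry once someone has withdrawn consent is sound. The last-contact rule goes further: it applies the same exclusion to people who have not refused data collection. A site that hears of a non-serious AE at that contact has one instruction not to enter it and another to enter it, and the more specific instruction is the one not to.

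At stake is the completeness of the AE tables. Non-serious events on the AESI list in SAP 14.13 (such as somnolence, fatigue or sedation), or the outcome of an AE already open, could be known to the site and missing from the analysis. The contact is likely to fall in the post-treatment period, and SAP 7.7.1 uses AEs from that period to assess withdrawal symptoms. The sponsor's continuous safety review under Protocol 10.9 could miss the same information.

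**Working it through.** The point turns mainly on the text, so the provisions are set side by side.

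1. **Scope of the exclusion (Protocol 5.9.2).** All withdrawals except death and loss to follow-up. This includes consent withdrawal, which has its own rule, and also investigator and sponsor withdrawal, where consent may stand.
2. **Scope of the AE rule (8.2.1; Table 1 footnote 7).** All AEs from consent to EOS, with no exception for withdrawn participants. Section 8.2.1 also foresees AEs coming to light in telephone calls, and Section 10.6.1 requires an eCRF for participants who do not complete the study.
3. **Can an EOS date reconcile the two?** One could argue that EOS falls at withdrawal, so that 8.2.1 no longer applies at the last contact. Neither document says which date is EOS for a withdrawn participant without an EOS visit. Section 8.2.1 also works by onset date: an AE that began before withdrawal but is first mentioned at the last contact falls under it on either reading. The conflict remains.
4. **Returned treatment.** The last contact is where unused capsules are collected. Section 6.1.6.4 sends the count to the eCRF, and Section 8.1.7 makes a mismatch consistent with overdose or medication error an AE to be recorded there. Section 5.9.2 read literally keeps both out.
5. **What is not exposed.** SAEs go to the sponsor on the SAE form (8.2.2). AEs entered at earlier visits stay in the eCRF. Participants who only stop treatment are not withdrawn (5.9.1) and are asked to attend EOT and follow-up visits.

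**Size.** The plan gives no figure to reproduce.

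- One participant among 60 per arm (Protocol 9.4): 1/60 = 1.7 percentage points.
- Illustrative range. Let w be the share withdrawn for reasons other than death or loss to follow-up, and q the chance that a new AE is first reported only at the last contact. Both are assumptions; the documents give neither. Expected participants missed per arm = 60 × w × q.
  - w = 5%, q = 5%: 60 × 0.05 × 0.05 = 0.15 (0.25 points).
  - w = 20%, q = 30%: 60 × 0.20 × 0.30 = 3.6 (6.0 points).
- Since w includes consent withdrawals, whose later data rightly stay out, the recoverable part is smaller than this range.

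**Site closures.** SAP Section 1 reports that "three sites withdrew from the study due to financial reasons related to COVID-19", and SAP 14.4 refers to "The 9 study participants forced to discontinue due to site closure". That is 9/120 = 7.5% of the planned sample. SAP Section 1 says that these participants finished the study, while SAP 6.1.6 describes them as withdrawing from it. Neither says whether they had EOT and EOS visits. SAP Section 1 points to Section 6 for their efficacy handling; SAP Section 7 does not mention them.

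**The case against.** The strongest reply is that the protocol already handles AE-driven exits elsewhere. Section 5.9.1 lets the investigator stop treatment because of an AE, and requires it when continued administration is against the participant's interests. It then keeps that person in the study with EOT and follow-up visits. Section 8.2.1 is unqualified, so a careful site would enter the AE anyway. On this view 5.9.2 is loose drafting with little practical effect.

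Much of this stands. A reader might infer from 5.9.2 that AEs are in fact lost, that they are lost in the people most likely to have them, and that incidences are therefore biased downwards or between arms. The documents do not support that. They give no withdrawal counts by reason or arm, and they document no investigator withdrawal. The main route for people with AEs is treatment discontinuation, which the last-contact rule does not touch.

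Nor do the 9 site-closure participants show such a loss. Their sites left for financial reasons, which is no sign of informative loss, and nothing shows that any of their AE data went unrecorded.

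The reply does not remove the conflict. Investigator withdrawal from the study rests on a best-interests judgment, and Section 7.2.5.7 has the investigator confirm suitability to remain in the study after certain C-SSRS answers. Safety-related study withdrawal is therefore foreseen. For those participants the two sections give opposite instructions, and nothing says which prevails.

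**Conclusion.** The contradiction is established from the text: 5.9.2 excludes last-contact data from the eCRF where consent stands, while 8.2.1 and Table 1 footnote 7 require AEs up to EOS to be recorded or reported. The consequence is a risk, not a demonstrated result. A site that follows 5.9.2 may leave out of the SAP 7.2 tables non-serious AEs, or AE outcomes, first learned at that contact.

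The size and direction of any loss are unknown. The range in the working rests wholly on assumed rates, and the 7.5% is a count of people who left because of site closure, not of people with missing AE data. This is an internal inconsistency worth correcting because the correction is cheap; it does not show that the safety results are biased.

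**What to change.** Reconcile 5.9.2 with 8.2.1, Table 1 footnote 7 and 6.1.6.4:

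- Limit the eCRF exclusion in 5.9.2 to participants who withdrew consent to further data collection.
- Where consent stands, have AEs, AE outcomes and returned-treatment counts from the last contact entered in the eCRF.
- State which date counts as EOS for a withdrawn participant without an EOS visit, so that the window in 8.2.1 and SAP 7.2 can be applied.
- In the CSR, state whether AE data up to the last contact were captured for the 9 site-closure participants. This can be done even if the protocol can no longer be amended.

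The cost is a short change to the protocol text and some extra data entry. No visit is added, because 5.9.2 already asks for the contact.
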